5.3 RECRUITMENT STRATEGIES AND CONSIDERATIONS

The recruitment efforts by the clinical study site will aim for a representative population with the following enrollment targets:

- Randomize no more than 60% of one sex
- Randomize no more than 50% White participants

Additional considerations for the day of the Study Visit:

- Participants must remove all nail polish or artificial nails on their hands to ensure that the PPG sensor can accurately detect the participant's pulse and blood volume changes.
- Participants must not eat on the test day prior to their visit.
*Extended fasting may be required if a later test time is scheduled.
- Participants must abstain from alcohol and caffeine by 8PM the night before their scheduled test day.
- Water is permitted.
*Compressions may induce the urge to urinate; regulated water consumption is recommended.
- Participants must not take diuretics the morning of the visit if it is scheduled in the morning. If it is scheduled in the afternoon, the diuretics can be taken as usual in the morning. Any other changes or modifications to any dosing schedules should be at the direction of the participant's physician.
- Participants should wear or bring loose-fitting clothing to be worn during the visit
 - For clothing tops, loose shirt or blouse is required to enable placement of EKG leads to enable the operation of the ACS NCP-2 predicate ECP device.
 - For clothing bottoms: shorts are required to allow better interfacing with the inflation cuffs/sleeves.
 - Ensure that clothing bottoms do not have non-removable buckles or metal/hard plastic accessories.
 - Cotton stockinettes will be made available to cover exposed skin on the legs.
- Participants should bring a written list of all current medications; dosage information included.

5.4 SCREEN FAILURES

In order for an individual to participate in the study, the participant must meet all Inclusion Criteria and none of the Exclusion Criteria. The participant must also be able to comply with the additional considerations listed in Section 5.3. Failure to meet eligibility will result in the individual being a Screen Failure. The reason for Screen Failure will be documented for each prospective participant.

6 STUDY DESCRIPTION

6.1 STUDY ECP DEVICE ADMINISTRATION – WAVE PRO SYSTEM

6.1.1 WAVE PRO ECP DEVICE DESCRIPTION

The Pression Wave PRO External Counter-Pulsation System applies compression to the calves, timed to peripheral diastole, to positively affect the patient's blood flow. It utilizes a pair of calf sleeves worn by the patient that are attached by tubing to a mobile compression control system, which houses the pneumatic, mechanical, electrical components, and an easy-to-use touch screen control interface. The patient's cardiac cycle is monitored by a pulse photoplethysmography (PPG) sensor worn and secured on the patient's finger by a clip and connected to the compression control system.

The calf sleeves inflate and deflate in synchrony with the phases of the patient's cardiac cycle, which is detected by the finger PPG sensor. These calf sleeves have a series of five inflatable bladders that are inflated sequentially, distally to proximally, towards the heart in the timeframe between heart beats. This compression generates retrograde arterial flow back to the heart, thus augmenting coronary flow during ventricular diastole.

6.1.2 WAVE PRO DEVICE TEST SESSION

This section pertains to the test session using the Wave PRO device with a participant that has been randomized.

- **Setup (approx. 10mins):** Time needed to get the participant ready for compressions will be recorded
 - Participant will be lying on the clinical bed with their back propped head-up at approximately 5° angle
 - Cotton stockinettes will be placed around the participant's legs between the knees and the ankles (if not already)
 - The clinical operator/technician will ensure that the Wave PRO is connected to an air supply source in the session room.
 - Clean air rated at 55 ± 1PSI.
 - Timer to record setup time will be started
 - The compression sleeves (with tubing attached) will be fitted around the participant's calves by a clinical operator/technician
 - The sleeves are differentiated by a left and a right sleeve
 - There are three different sleeve sizes (small, medium, large)
 - The sleeves are placed between the participant's ankles and knees
 - with the compression bands wrapped around the calf muscle
 - with the tubing ports on the medial side of the legs, pointing towards the feet
 - The compression sleeves should be snug against the participant's legs (tight but comfortable)

- The clinical operator should not be able to fit an index finger between the Compression Sleeve and the legs, but should not be so tight that the participant can feel their pulse through their leg
- **Rest (supine), blood pressure and heart rate (approx. 5 mins):** Participant should be completely set up and then asked to lie back and relax
 - Amount of time it took to set up will be recorded
 - The participant's systolic/diastolic pressures and heart rate will be recorded
- **Baseline PPG (2 mins):** With the Wave PRO system powered ON and on standby (not compressing), recording will be conducted to capture baseline PPG waveforms using the dedicated BIOPAC data acquisition system
 - Two PPG sensors will be placed on the participant's hand:
 - One for the Wave PRO
 - One for the dedicated Data Acquisition System
 - The sensors should be placed on the index (Wave PRO) and middle fingers (BIOPAC) on the right hand (if the Data Acquisition System signal is noisy, the sensor can be switched to another finger on the same hand)
 - The User Pause Button will be given to the participant to hold in the left hand
 - The User Pause Button allows the participant to temporarily stop the compressions at any time.
- **Compression (10 mins):** Participants will be asked to relax and minimize all movement and the operator will begin compressions
 - To be able to start compressions, the clinical operator should make sure of the following:
 - The E-Stop on the front panel is disengaged
 - System Check checklist items on the screen all have blue checkmarks
 - "Next" button has been pressed.
 - 60 minutes Treatment Time has been selected
 - "Start Treatment" button has been selected
 - PPG waveform data will be recorded on the BIOPAC data acquisition system.
 - Mark pre-compression baseline PPG start and end using the study laptop
 - Mark compression start and end using the study laptop
 - Mark post-compression PPG start and end using the study laptop
- **Stop compressions:** The clinical operator/technician will stop the delivery of compressions after 10mins has elapsed by pressing the "Cancel Treatment" button.
- **Post-Compression PPG (2 mins):** At the conclusion of the 10 minute ECP session, a post-compression PPG signal will be recorded
 - Participant will be asked to relax and minimize all movement.
- **End-of-Session procedure, blood pressure and heart rate, device-related questionnaire:** The clinical operator/technician will perform the following:
 - The participant's systolic/diastolic pressures and heart rate will be recorded
 - Participant questionnaire related to the ECP device will be conducted
 - Wave PRO system will be turned off (if applicable)

- Air supply line to the Wave PRO system will be disconnected (if applicable)
- Sensors will be removed from the participant's fingers
- Compression sleeves will be removed from the participant's calves
- If this is the second test session, an observation period of approx. 10 minutes should be made available for each participant

6.2 PREDICATE ECP DEVICE ADMINISTRATION – APPLIED CARDIAC SYSTEMS (ACS) NCP-2 EXTERNAL COUNTER-PULSATION (ECP) SYSTEM

6.2.1 ACS NCP-2 ECP DEVICE DESCRIPTION

The Applied Cardiac Systems (ACS) NCP-2 is an FDA cleared ECP system (K042413) indicated for the treatment of chronic stable angina. The ACS system is similar to other commercially available ECP devices on the market. It utilizes three inflation cuff sets (calf, thigh, buttocks) to deliver sequential compressions timed to the cardiac cycle. Compressions are timed to the patient's EKG and treatment efficacy is measured using a PPG sensor. The user interface of the ACS NCP-2 device requires the clinical operator/technician to input inflation and deflation timing of the cuffs and must input pressure settings manually. As a result, the clinical operator/technician must have an understanding of EKG and PPG waveform shapes to ensure the input parameters are appropriately set.

- **Compressions (10mins):** The clinical operator/technician will begin compressions.
 - The ACS NCP-2 PPG sensor will be placed on the participant's right pointer finger
 - The clinical operator/technician will adjust the device pressure and the inflation and deflation timing based on the red and blue colored marker bars, respectively, on the monitor
 - The timing (red and blue colored marker bars) needs to be adjusted to generate a PPG waveform that has the appropriate shape (refer to IFU for inflation and deflation timing and resulting PPG waveform shapes)
 - As a starting point, the red colored region should start at the peak of T-wave (inflation) and the blue colored region should terminate just prior to the subsequent P-wave (deflation)
 - The 10 minutes of compressions start once the "Start Pump" button has been clicked (i.e., includes timing search)
 - PPG waveform data will be recorded on the ACS NCP-2 software (waveforms are only recorded when the pump is running)
 - Compression pressure will be increased in small increments until a maximum of 3 PSI is reached, per the ACS software readout
 - In accordance with pressure settings for the first day of ECP treatment per the predicate device IFU
 - 3 PSI will be reached as fast as possible along with the correct inflation/deflation timing

- **Stop compressions:** Compressions will be concluded by pressing the “Pump Start” button again after 10 mins have elapsed
 - Proper steps to exit out of the treatment screen will be followed to prevent loss of data
 - The participant’s profile will be revisited immediately to ensure that the test data was saved (Full Disclosure screen)
- **End-of-Session procedure:** The clinical operator/technician will perform the following:
 - The participant’s systolic/diastolic pressures and heart rate will be recorded
 - Participant questionnaire related to the ECP device will be conducted
 - ACS NCP-2 will be turned off (if applicable)
 - EKG leads and electrodes will be removed from the participant
 - Sensors will be removed from the participant’s finger
 - The three compression cuff sets will be removed from the participant
 - If this is the second test session, an observation period of approx. 10 minutes should be made available for each participant

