4 STUDY DESIGN

4.1 OVERALL DESIGN

Potential study participants will be recruited per standard practices of the clinical research facility (may include advertising/publicity). Participants will be consented prior to any study related assessments/procedures. Only eligible participants that meet the required criteria (inclusion/exclusion) will be enrolled in the study and subsequently randomized to the ECP devices. Overall study design is shown in **Figure 1**. For the Wave PRO, PPG waveforms will be collected with an independent data acquisition system, BIOPAC (Goleta, CA). The predicate device has onboard data capture and analysis functionalities.

Steps for the Clinical Site for each randomized participant (see Section 6):

- For the Wave PRO: setup (recorded time), rest period (supine, recorded blood pressure and heart rate), pre-compression baseline PPG (recorded on BIOPAC), compression period (automated inflation/deflation tuning, PPG recorded on BIOPAC), post-compression PPG (recorded on BIOPAC), and end of session procedures (recorded blood pressure and heart rate, Wave PRO questionnaire administered).
- For the predicate ACS NCP-2: setup (recorded time, participant profile created), rest period (supine, recorded blood pressure and heart rate), compression period (manual inflation/deflation tuning required, PPG recorded on predicate device), and end of session procedures (recorded blood pressure and heart rate, predicate questionnaire administered).

There will be a 20-minute washout period between the two ECP device sessions, requiring the participant to walk around (no strenuous or high-intensity activities). An observation period will be required after the last test session. A final questionnaire will be conducted during the follow-up call the next day.

Signal Processing steps include (see Section 6):

- For the Wave PRO: average DA ratio will be measured using an R script that processes the BIOPAC waveform data at the 8th minute of compression (i.e., minute 7 to minute 8 of compressions). Average systolic amplitude of the last 10 waveforms of baseline before compressions and the average amplitude of the systolic amplitude of the first 10 waveforms during compressions will be recorded for systolic unloading calculations.

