9.3.3 SECONDARY EFFECTIVENESS ENDPOINTS**Secondary Effectiveness Endpoint 1:**

The level of systolic unloading will be recorded for the Wave PRO based on the systolic peaks during compressions compared to baseline of the PPG data (before compressions and captured using the independent data acquisition system). Systolic unloading is the ratio of the systolic peak during compressions divided by baseline systolic peak. Previous studies that measured systolic pressure using coronary catheterization found that “peak aortic systolic pressure decreased 11% during ECP”⁴. Based on these findings, systolic unloading is expected to be similar when measured via PPG. Systolic unloading will be calculated as the ratio of the average systolic amplitude of the last 10 waveforms of baseline PPG before compressions divided by the average amplitude of the systolic amplitude of the first 10 waveforms during compressions.

Analysis cohort: mITT participants with paired data.

Analysis methods:

Descriptive statistics will be used to summarize systolic unloading including mean, standard deviation, median, and minimum and maximum. Additionally, the count and percentage of participants who have systolic unloading values $\geq 11\%$.

Secondary Effectiveness Endpoint 2:

Number of participants that complete 10 mins of each of the ECP devices (Wave PRO and predicate ECP device).

Analysis cohort: mITT participants with an attempt to receive Wave PRO ECP.

Analysis methods:

The count and proportion of participants that successfully completed the planned 10 min of Wave PRO ECP and the predicate ECP device will be summarized.

Secondary Effectiveness Endpoint 3:

Participant comfort level with the Wave PRO and predicate ECP device, assessed at the conclusion of each ECP session (i.e., using a Likert scale).

Analysis cohort: mITT participants

Analysis methods:

Descriptive statistics will be used to summarize the participant's comfort by ECP device.

Secondary Effectiveness Endpoint 4:

Time to set up a participant (i.e., sleeved up and sensors attached) and ready to start treatment.

Analysis cohort: mITT participants

Analysis methods:

Descriptive statistics will be used to summarize the setup time by ECP device.

Secondary Effectiveness Endpoint 5:

Participant preference for one of the two ECP systems (assuming 35 hours for a full course of ECP).

Analysis cohort: mITT participants

Analysis methods:

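### The comfort rating is not timed alike on the two devices: Wave PRO schedules a 2-minute still recording after compressions stop, the predicate only an untimed screen exit and save check

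*Combined protocol and SAP*

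**What the plan says.** Section 9.3.3 defines the endpoint as "Participant comfort level with the Wave PRO and predicate ECP device, assessed at the conclusion of each ECP session". It specifies a Likert scale and descriptive statistics by device in the mITT participants. It does not say how long after compressions stop the rating is to be taken.

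For Wave PRO, Section 6.1.2 stops compressions at 10 minutes and then says: "At the conclusion of the 10 minute ECP session, a post-compression PPG signal will be recorded". This step is scheduled for 2 minutes, with the participant asked to keep still. Only then comes the step headed "End-of-Session procedure, blood pressure and heart rate, device-related questionnaire". The overview in Section 4.1 gives the same order: "post-compression PPG (recorded on BIOPAC), and end of session procedures (recorded blood pressure and heart rate, Wave PRO questionnaire administered".

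For the predicate, Section 4.1 goes from one to the other directly: "compression period (manual inflation/deflation tuning required, PPG recorded on predicate device), and end of session procedures". Section 6.2.2 adds two operator tasks after the pump stops. The treatment screen is exited by the proper steps, and the participant's "profile will be revisited immediately to ensure that the test data was saved (Full Disclosure screen"). Blood pressure and heart rate follow, and then "Participant questionnaire related to the ECP device will be conducted". None of these steps has a stated duration.

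**The concern.** A comparison of a subjective rating between two devices should use the same measurement time on both. Here one device has a fixed 2-minute pause before the rating and the other has whatever time the operator needs to close and check a file.

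Three features make this worth correcting:

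- Comfort is a named secondary endpoint reported by device. Section 2.3.2 already anticipates better comfort with Wave PRO.
- Section 6.6 states that neither participants nor operators can be blinded, so a subjective rating has little other protection.
- The crossover design does not help, because the difference in timing goes with the device in both sequences.

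If discomfort eases once compressions stop, the device rated later would look better for a reason unrelated to the device. After data collection the question could not be answered, because the plan does not call for the time of the rating to be recorded.

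**Working it through.** The plan gives no figure for this interval, so there is none to reproduce. The check sets the two session sequences side by side.

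| Step after compressions stop | Wave PRO (6.1.2) | Predicate (6.2.2) |
|---|---|---|
| Still recording, no compression | 2 min, scheduled | not scheduled |
| Exit screen and check saved data | not listed | x min, duration not given |
| Blood pressure and heart rate | m min, not given | m min, not given |
| Comfort questionnaire | next | next |
| Sleeves or cuffs removed | after questionnaire | after questionnaire |

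**Size of the gap.** Assume that blood pressure and heart rate take the same time m on both devices. Time from compression stop to rating is then 2 + m on Wave PRO and x + m on the predicate, so

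gap = (2 + m) − (x + m) = 2 − x minutes.

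The documents do not give x. Over an assumed range:

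- x = 0: gap = 2 minutes, Wave PRO rated later
- x = 1: gap = 1 minute, Wave PRO rated later
- x = 2: gap = 0
- x = 3: gap = −1 minute, predicate rated later

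**Does randomized order remove it?** Let τ be the true comfort difference (Wave PRO minus predicate), b the shift caused by unequal rating times, and p the effect of being in the second period rather than the first.

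- Wave PRO first: observed difference = τ + b − p
- Predicate first: observed difference = τ + b + p
- Average of the two sequences: τ + b

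The period effect cancels. The timing shift does not.

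**Does it reach the primary endpoint?** No. The DA ratio is taken between minutes 7 and 8 of compression (Section 9.3.1), before the interval in question begins.

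**Is the 2-minute recording needed before the rating?** No listed endpoint uses it. The DA ratio uses minute 7 to 8. Systolic unloading uses the last 10 baseline waveforms and the first 10 waveforms during compressions (Section 9.3.3). The predicate has no counterpart because its software records only while the pump runs (Section 6.2.2). That explains the missing recording, but it does not prevent a matched wait.

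**The case against.** The best defence is that the consequence is unproven and the stakes are low. The questionnaire wording is not in the documents. If the item asks how the session felt as a whole, a delay of a minute or two may change nothing. Comfort has no test, margin or success criterion. Tolerability is also captured elsewhere: discomfort during sessions is recorded (Section 2.3.1), completion of 10 minutes is a secondary endpoint, and a survey is repeated a day later (Section 8.3). All of this stands and keeps the point minor. It does not make the two rating times equal.

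A reader might also infer four stronger things, which the documents do not support:

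- **That the predicate is rated at once, giving a gap of a full 2 minutes.** Section 6.2.2 puts the screen exit and save check first, and blood pressure and heart rate precede the questionnaire on both devices. The predicate delay is unknown, not zero.
- **That the comparison is shown to be biased toward Wave PRO.** This needs both x below 2 minutes and a rating that improves over the interval. Neither is documented.
- **That post-session blood pressure and heart rate comparisons are compromised.** They are not named endpoints, and Section 9.3 plans no analysis of them.
- **That the pre-compression periods must also be matched.** Wave PRO does have an extra step in which "recording will be conducted to capture baseline PPG waveforms using the dedicated BIOPAC data acquisition system", but both rest periods are only approximate, and nothing links this difference to a result.

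**Conclusion.** The point holds as an unstandardized measurement time for one descriptive secondary endpoint. The interval before the comfort rating differs by about 2 − x minutes between devices, with x unknown and equal time assumed for blood pressure and heart rate. The difference is tied to device in both sequences. It could favour Wave PRO if x is under 2 minutes and discomfort fades after compressions stop. The effect on the rating cannot be sized from the documents, so no figure in scale points is offered. The primary analysis and the sample size of 44 are untouched. This is an inexpensive improvement, not a threat to the trial's main conclusion.

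**What to change.** In Sections 6.1.2 and 6.2.2, administer the comfort item at the same stated time after compressions stop on both devices. There are two ways to do this:

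1. Add a matched 2-minute still period on the predicate, counted from pump stop, so that the screen exit and save check fall inside it. This adds about 2 minutes to a visit of 2.5 to 3 hours (2/150 = 1.3% to 2/180 = 1.1%).
2. Ask the Wave PRO comfort item before the post-compression recording. This only delays a recording that feeds no listed endpoint. The predicate item must be fixed to the same stated time. Otherwise the gap changes from 2 − x to 0 − x = −x, and the predicate is rated later.

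The first is simpler, because it leaves the immediate save check where it is. Under either option, record the time compressions stop and the time of the rating on the CRF, so that the interval can be reported by device. The end of Wave PRO compressions is already tagged in the recording (Section 6.3.2). Neither option needs more participants or equipment.

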6.3 DATA ACQUISITION WAVE PRO

6.3.1 BIOPAC MP35 DATA ACQUISITION SYSTEM DESCRIPTION

The BIOPAC MP35 Data Acquisition system paired with the BSL 4.1 software will serve as the dedicated PPG waveform and data extraction system to acquire waveforms that will subsequently be used to calculate DA ratio and select secondary endpoints as a result of Wave PRO compressions. The MP35 is a four channel system with a 24-bit A/D sampling resolution. The MP35 is capable of recording 100,000 samples per second.

The BIOPAC SS4LA PPG Transducer, which connects to the 9-pin female DSUB connector on the MP35, will be attached to the participant’s finger using the built-in hook-and-loop strap to capture PPG signals. The SS4LA is a reflectance type PPG sensor that utilizes a matched infrared emitter and photo diode to detect changes in blood density due to blood pressure fluctuations. The emitter/detector wavelength is 860nm \pm 60nm, with a built-in low pass filter cutoff wavelength of 800nm.

